8.3 Secondary Endpoints

The secondary study endpoints will be examined descriptively in both the ITT and PP populations.

8.4 Sample Size and Power

With a hypothesized incidence rate of 75% for revascularization post-procedure and desired power of 80%, and using an exact binomial test with a nominal 0.025 one-sided significance level (equivalent to a two-sided $\alpha=0.05$), the required evaluable sample size for primary efficacy is 135. For primary safety, under a hypothesized incidence rate of 20% for the composite endpoint and desired power of 80%, the corresponding required evaluable sample size is 153. As 153 is the larger of these two values, this will be the required evaluable sample size to reach at least 80% power for both effectiveness and safety analyses. Considering a 5% loss to follow-up rate, which is consistent with the observed follow-up rate to date, the Sponsor proposes to adjust the total sample size to 160.

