Objective	The objective of the TIGER Study is to evaluate the safety and effectiveness of the Tigertriever device in restoring blood flow in the neurovasculature by removing thrombus in patients experiencing ischemic stroke due to a large vessel occlusion (LVO). This study is designed to support substantial equivalence to approved and marketed products such as the Solitaire or Trevo Retriever.
Study Design	This study is a US and EU, multicenter, single arm, prospective IDE study to evaluate the safety (defined as all cause mortality) and effectiveness of the Tigertriever Revascularization Device in Acute Ischemic Stroke (AIS) patients ineligible for IV t-PA treatment or who fail IV t-PA therapy.
Device Description and Intended Use	Tigertriever is a CE marked mechanical revascularization device. The Tigertriever Revascularization Device is indicated to restore blood flow by removing thrombus from a large intracranial vessel in patients experiencing ischemic stroke within 8 hours of symptom onset. Patients who are ineligible for IV t-PA or who fail IV t-PA therapy are candidates for treatment.
Primary Endpoints	
Effectiveness: Successful reperfusion, defined as mTICI Score $\geq 2b$ at the end of the Tigertriever revascularization procedure.
 
Safety: Composite of all-cause mortality at 90 (± 14) days and symptomatic intracranial hemorrhage (sICH) within 24 (18-36) hours of the study procedure.

Secondary Endpoints	
Effectiveness:
 
 • Good Clinical Outcomes- Percentage of participants with a modified Rankin Scale (mRS) score of ≤ 2 at 90 (± 14) days post treatment.

	
 • Successful reperfusion (defined as mTICI 2b or better) at first pass. • Health related quality of life (EQ-5D score) • Degree of disability (Academic Medical Center – Linear Disability Scale score) 
Safety:
 
 • Any asymptomatic intracranial hemorrhage within 24h (18h-36h) of the procedure • Neurological deterioration (≥ 4-point increase in NIHSS score) at 24h (18h-36h) post-procedure. • Embolization to previously uninvolved vascular territories,

Number of Subjects:
 
The maximum Sample size is 160, including up to 60 lead-in Subjects (up to 4 per site). Lead-in Subjects will be used for endpoint analysis.
	
Number of Study Centers:
 
Up to 25 centers total in the US and EU

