MR CLEAN	21%	7.7%
ESCAPE	10%	3.6%
REVASCAT	18.4%	4.9%
SWIFT PRIME	9%	0%
Pooled estimate	18.2%	4.2%

The performance goal (PG) for the composite primary safety endpoint of all-cause mortality and symptomatic intracranial hemorrhage is defined using the incidence of the individual endpoints in the six trials cited above. For this purpose, the sum of the two pooled event rates is $18.2\% + 4.2\% = 22.4\%$; however, as sICH is known to be associated with mortality, this is likely an overestimate of the composite event rate. For conservatism, therefore, only half of the sICH rate will be added to mortality as representing distinct subjects, resulting in a pooled event rate of 20.4% . Adding to this a statistical margin of 10% gives a PG of $20.4\% + 10.4\% = 30.4\%$.

The resulting null and alternative statistical hypotheses are therefore as follows:

$$H_0: p > PG$$

$$H_A: p \leq PG,$$

where $PG = 20.4\% + 10.4\% = 30.4\%$ as above and p is the observed incidence of revascularization post-procedure with the Tigertriever device. The hypothesis test will be performed at an overall two-sided alpha level of 0.05 using exact binomial methods, in which the upper confidence bound on the observed incidence of revascularization is compared to the PG.

The primary endpoint analysis will be performed using the intent to treat (ITT) population. The ITT population will consist of all enrolled subjects who had at least one Tigertriever device attempt/deployment irrespective of major protocol violation. The per protocol (PP) population is defined as ITT patients who do not have major protocol violations. A major protocol violation includes when a subject does not meet inclusion/exclusion criteria. All protocol violations will be reported.

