8.6 Missing Data

The number and proportion of Subjects eligible for and compliant with each follow-up examination will be presented. Subjects who withdraw from the study will be tabulated with reasons for withdrawal. Since the primary efficacy endpoint is defined immediately post-procedure, the amount of missing data for this endpoint is anticipated to be very low and necessarily unrelated to subsequent losses to follow-up.

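### Section 8.4's total of 160 falls one evaluable subject short of its own requirement: 5% loss leaves 152, not 153, and exact safety power at 152 is 79.9%

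*Combined protocol and SAP*

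**What the plan says.** Section 8.4 (Sample Size and Power) sizes both primary endpoints "using an exact binomial test with a nominal 0.025 one-sided significance level". It arrives at 135 evaluable subjects for effectiveness and 153 for safety. Of the larger figure it says "this will be the required evaluable sample size to reach at least 80% power for both effectiveness and safety analyses". It then moves from evaluable to enrolled subjects. The allowance for loss is worded as "Considering a 5% loss to follow-up rate, which is consistent with the observed follow-up rate to date". On that basis, the section ends by stating that "the Sponsor proposes to adjust the total sample size to 160".

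The Protocol Summary (Number of Subjects) presents 160 as a maximum, lead-in subjects included, so there is no stated room to enrol more.

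Section 8.6 (Missing Data) separates the two endpoints. For effectiveness it says that "the amount of missing data for this endpoint is anticipated to be very low and necessarily unrelated to subsequent losses to follow-up". It gives no rule for a missing 90-day safety outcome.

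**The concern.** A total sample size is normally the evaluable requirement divided by one minus the loss rate, rounded up. The total of 160 does not come from 153 and 5% in that way. It leaves one subject fewer than the number the section has just called required.

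The gap is small, but 153 is not an arbitrary number here. By exact calculation it is the smallest sample size from which safety power stays at or above 80%, and 152 is the last value below. At its own stated loss rate, the plan therefore lands just under the threshold it promises to meet. Anyone reproducing section 8.4 will find that its closing figure does not deliver the stated power for safety.

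**Working it through.** **Inputs**

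- Safety performance goal (null rate) 30.4%: section 8.2.
- Assumed true safety event rate 20%, target power 80%: section 8.4.
- Test: exact binomial, one-sided 0.025 (sections 8.2 and 8.4).
- Effectiveness, as a cross-check: performance goal 63.4% (section 8.2), assumed rate 75% (section 8.4).
- Loss to follow-up 5%, total 160: section 8.4. The 160 is a maximum in the Protocol Summary.

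**Step 1. Reproduce the plan's evaluable numbers.** For safety, the trial passes with X ≤ c events, where c is the largest count with P(X ≤ c | n, 0.304) ≤ 0.025. Power is P(X ≤ c | n, 0.20).

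| Evaluable n | Pass limit c | Exact one-sided alpha | Power |
|---|---|---|---|
| 150 | 34 | 0.0222 | 82.2% |
| 151 | 34 | 0.0197 | 81.1% |
| 152 | 34 | 0.0175 | 79.9% |
| 153 | 35 | 0.0243 | 83.9% |
| 156 | 35 | 0.0170 | 80.7% |
| 160 | 36 | 0.0165 | 81.4% |

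No sample size above 152 has power below 80%, so the plan's 153 reproduces. The mirror-image calculation for effectiveness gives 78.9% at 134 and 82.8% at 135, with 134 the last value below 80%, so the plan's 135 reproduces by the same rule.

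**Step 2. Apply the 5% loss.**

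- From the total downwards: 160 × 0.95 = 152.
- From the requirement upwards: 153/0.95 = 161.05, so 162. At 161 the expected evaluable number is 161 × 0.95 = 152.95.
- The cruder inflation, 153 × 1.05 = 160.65, rounds up to 161.

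Neither formula gives 160 unless it is rounded down. With 160 enrolled, 153 evaluable needs at most 160 − 153 = 7 losses, and 7/160 = 4.4%.

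**Step 3. Why power drops at 152.** At 152 the pass limit is still 34 events, because 35 would give an alpha of 0.0272, above 0.025. At 153 the limit moves to 35 and power rises by about four points. Between such steps, each added subject lowers power slightly, which is why 150 and 151 do better than 152.

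**Step 4. Treat the loss as random.** Assume each of 160 subjects is lost independently with probability 5%, so evaluable n follows Binomial(160, 0.95). Then:

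- P(n ≥ 153) = 44.9%.
- P(n falls where exact safety power is below 80%) = 27.7%.
- Mean safety power = 81.4%.

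**Step 5. Effectiveness.** The outcome is read at the procedure. At n = 160 the trial needs 114 or more successes and power is 88.1%. Even at 152 it is 84.8%.

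**The case against.** The strongest reply is that nothing practical follows. A power of 79.9% prints as 80%, average power under random loss is above target, and enrolling 162 would raise that average only to 82.0%. The 5% is a round planning figure, and any loss up to 4.4% delivers 153. All of this stands. It sets the weight of the point but does not make the three figures agree, because 5% is the rate the plan states.

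A second reply is that a subject lost to follow-up is not always unevaluable for safety. The endpoint includes symptomatic hemorrhage at 24 hours, and section 5.1.3 keeps data obtained before withdrawal, so a subject who had already had an event would still count. If the 5% applied only to the 80% without an event, about 0.05 × 0.80 × 160 = 6.4 subjects would be unevaluable and 153.6 would remain. This is a fair reading of how the data might fall, but section 8.4 itself uses loss to follow-up as the whole gap between total and evaluable. On that footing the answer is 152. The restated text should say so openly.

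A third reply is that the safety performance goal is itself unsettled. In section 8.2, 18.2% plus half of 4.2% is 20.3%, and 20.4% plus 10.4% is not 30.4%. With a goal of 30.3%, power is 79.9% at 152 and 78.7% at 153, and sustained 80% power starts at 158. That is a separate matter and does not rescue 160. The figures here hold for 30.4%, the goal the plan uses and the one from which 153 reproduces.

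**Conclusion.** The concern holds as a small arithmetic slip. On the plan's own inputs, 160 enrolled with 5% loss gives 152 evaluable subjects for safety, one fewer than the 153 required. Exact safety power is then 79.9%, about 0.1 point under the promised 80%. The conclusion rests on a performance goal of 30.4%, a true event rate of 20%, a one-sided exact test at 0.025, and every lost subject being unevaluable for safety. It does not show an underpowered trial, and effectiveness is not touched. It is of the lowest severity: the stated size and power need restating, while the design can stay as it is.

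**What to change.** Keep 160 and replace the end of section 8.4 with text along these lines:

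> With 160 enrolled, 153 evaluable for safety is reached if no more than 7 subjects (4.4%) lack the safety outcome. At 5% loss, counting every lost subject as unevaluable for safety, 152 are evaluable and exact power for safety is 79.9% (about 80%). Effectiveness is assessed at the procedure in up to 160 subjects, with exact power of about 88%. These are per-endpoint figures.

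The cost is two or three sentences. No patients are added, and the test, the performance goals and the maximum of 160 do not change. If the safety performance goal in section 8.2 is corrected, recompute these figures at the same time.

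The alternative is to raise both the total and the stated maximum to 162. That restores 153 at 5% loss but adds two patients for little gain in average power (81.4% to 82.0%).

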8.5 Subgroup Analysis

Analysis of the primary endpoints will be conducted in subgroups of interest, including subgroups defined by device used (Tigertriever versus Tigertriever 17) and subgroups defined by subjects ineligible for IV-tPA administration versus those failing IV-tPA, subjects age 18-69 vs 70-85, and target occlusion location (ICA vs M1 vs M2 vs posterior circulation),

8.6 Missing Data

The number and proportion of Subjects eligible for and compliant with each follow-up examination will be presented. Subjects who withdraw from the study will be tabulated with reasons for withdrawal. Since the primary efficacy endpoint is defined immediately post-procedure, the amount of missing data for this endpoint is anticipated to be very low and necessarily unrelated to subsequent losses to follow-up.

8.7 Poolability Across Investigational Sites

This is a multi-center clinical study, with standardization of Subject enrollment, data entry and adverse event reporting. All investigational sites will follow the requirements of a common protocol, data collection procedures and forms. To present the data from this clinical study in a summary form, a comparison of the primary endpoints across sites will be completed to determine if the generated data can be pooled.

The relevant statistical test for both primary efficacy and primary safety will be Pearson's chi-square test across sites; a p-value less than 0.10 will be considered cause for investigation of non-poolability.

8.8 Interim Analysis

No interim analysis is planned.

8.9 Deviations from the Statistical Plan

Any departure or deviation from these planned statistical methodologies will be documented and discussed in the Statistical Analysis Plan that will include the statistical rationale for change.

9. RISK/BENEFIT ANALYSIS

A risk analysis according to ISO 14971 (Application of Risk Management to Medical Devices) has been conducted as part of the CE Marking process. Risks have been minimized or eliminated through appropriate design control, and confirmed by pre-clinical bench, laboratory and animal testing.

9.1 Main Potential Benefits of the Tigertriever:

Vessel recanalization is one of the strongest predictors of improved functional outcomes and reduced mortality in ischemic stroke patients⁴⁶. It has been further shown that if the vessels can be quickly recanalized, the correlation with good outcomes is even more powerful⁴⁷.

There are no guaranteed benefits from participation in this study; however, it is possible that treatment with the Tigertriever Device may improve blood flow through the treated artery. This may result in Subjects experiencing fewer or less severe long term ischemic stroke symptoms and less final disability.

Information gained from the conduct of this study may be of benefit to other persons with the same medical condition and age ranges. Study results will be analysed by subgroups based on age.

The following features incorporated into the design of the device, enable the physician to have full control on the device and the process:

- Fully radiopaque, full visibility under fluoroscopy.

- Ability of the physician to control the shape of the mesh and lock it in the required position.

9.2 Main Potential Risks:

The main possible complications that have been identified in the risk management process for the Tigertriever are risks that are known for any catheterization and thrombectomy procedure, including, but not limited to: hematoma and hemorrhage at puncture site, infection, dissection, vessel perforation, emboli, thrombus, hemorrhage, ischemia, vasospasm, vascular occlusion, pseudo aneurysm formation, post procedure bleeding, distal thrombus formation, distal embolization including to a previously uninvolved territory, adverse allergic reaction to antiplatelet/anticoagulation agents or contrast media, device deformation/collapse/fracture/malfunction, arteriovenous fistula and neurological deficits, including stroke and death. Additional risks might include burning sensation, delay in procedure, (resulting to increase use of contrast, fluoroscopy and anesthesia), peripheral ischemia, incomplete treatment, (unable to treat or no improvement or major injury), organ impairment, fever, local or systemic inflammatory response, shock (traumatic, anaphylactic, hemorrhagic or septic), vassal stenosis or restenosis. General discomfort, tenderness or pain, standard risk of being under general anesthesia (nausea, vomiting), and ionizing radiation exposure.

9.2.1 Minimization of Risk

- The Tigertriever is intended to be used only by physicians who have received appropriate training in interventional neuro-endovascular techniques and neuro thrombectomy techniques.
- The design of the Tigertriever (material used, its visibility, the ability to control it, etc.) minimizes the potential risk to damage blood vessels and enables short and quick procedure.
- Detailed instructions for use that define the procedural steps, warnings of misuse, precautions and guidance for appropriate use of the device will be provided with the device.
- The Tigertriever will be deployed only in patients in whom an endovascular thrombectomy procedure has already been determined as clinically indicated by their clinical physicians. Accordingly, procedure-related risks, including risks of conscious sedation or general anesthesia, arterial puncture and sheath placement, exposure to ionizing radiation, and intra-procedural anticoagulation, are inherent to the patient's clinical state and indicated course of therapy, and not the trial. Only device-specific risks, such as risks of device deformation/collapse/fracture/malfunction are specific to the trial.

The estimated risks for all identified hazards all meet the defined criteria for risk acceptability. As a result the estimated risk for all identified hazards remains as low as possible.

All of the above suggests that the advantages of mechanical revascularization using the Tigertriever in acute ischemic stroke outweigh its disadvantages and risks.

10. DEVIATIONS FROM THE CLINICAL INVESTIGATION PLAN

10.1 Protocol Deviations

A protocol deviation is defined as any change or alteration from the procedures stated in the clinical investigation plan, consent document, recruitment process, or study materials (e.g. questionnaires) that were originally approved by the IRB/EC where the change or alteration itself is not IRB/EC approved. Protocol deviations can be either major or minor.

All protocol deviations must be reported to Rapid Medical or their authorized representatives (study monitors) through the eCRF protocol deviation form. All deviations, regardless of whether medically justifiable (Subject's safety) or pre-approved by Rapid Medical and/or the IRB/EC of record, shall be reported. In addition, the Investigator is required to adhere to IRB/EC of records' procedures for reporting protocol deviations.

Prior approval for deviation from the CIP shall be obtained by the Investigator from Rapid Medical, except in situations where necessary to protect the safety of a Subject (emergency) or for situations beyond the Investigator's control such as Subjects missing scheduled follow-up visits. Approval for deviations shall be documented in writing and maintained in the Investigator and clinical study management files.

Per 21 CFR §812.140 (a) (4), Investigators are required to maintain accurate, complete and current records, including documentation showing the dates of, and reasons for, each deviation from the CIP. Failure to comply with the CIP may result in Investigator termination of participation [21 CFR §812.46 (a)] in the TIGER study.

10.2 Major and Minor Protocol Deviations

A Major protocol deviation is defined as an event that resulted in an increased risk to a subject or others; affected the right, safety or welfare of a subject; or affected the integrity of the study. Major protocol deviations include, but are not limited to:

- Failure to obtain informed consent prior to patient enrollment
- Enrolled patient did not meet the inclusion/exclusion criteria
- Source data permanently lost

- Introduction of rescue therapy prior to attempting revascularization with Tigertriever for three passes.

Any other events that do not comply with the requirements of the protocol will be considered Minor protocol deviations.

Examples of Minor protocol deviations are:

- Incorrect version of the informed consent form used.
- Patient did not attend follow-up visit or follow-up visit was outside the required window.

11. SAFETY AND ADVERSE EVENTS

Safety of study Subjects is of critical importance for the TIGER study. Site Investigators are responsible for the safety of Subjects under his/her care. In order to more clearly understand data and potential confounders, assessment of all Adverse Events observed by the site investigators will be recorded in the case report form and reported to the Data and Safety Monitoring Board for period review.

11.1 Adverse Event Data Collection

Recording of adverse events commence from time that a Subject is appropriately consented and culminate through the 90-day (\pm 14) follow up. All available information related to the AE must be obtained by the Investigator so that proper determination of causality and outcome can be made and classification as a SAE can be made if warranted. Adverse Events will be documented on the appropriate eCRF. Data captured include the event description, onset, resolution status, seriousness, severity, causality (if known) and treatment, if done. The Investigator will follow all AEs until resolution or completion of the 90-day follow-up.

11.2 Definitions

11.2.1 Adverse Events

Per ISO 14155:2011 section 3.2, an Adverse Event is any untoward medical occurrence, unintended disease or injury, or untoward clinical signs (including abnormal laboratory findings) in Subjects, users or other persons, whether or not related to the investigational medical device.

In the event that a Subject participates in the TIGER Study with signs of prior disease and/or symptoms, these conditions would not be considered AEs unless the condition recurs after the Subject has recovered from the previously occurring condition or the condition worsens in intensity or frequency during participation in the TIGER Study.

11.2.2 Adverse Device Effect

Per ISO 14155:2011 Section 3.1, an Adverse Device Effect (ADE) is any AE related to the use of an investigational medical device.

11.2.3 Serious Adverse Events

Per ISO 14155:2011 Section 3.37, an SAE is an AE that:

1. Led to death,
2. Led to serious deterioration in the health of the Subject, that resulted in:
 - a. a life-threatening illness or injury, or
 - b. a permanent impairment of a body structure or a body function, or
 - c. in-patient or prolonged hospitalization, or
 - d. medical or surgical intervention to prevent permanent life-threatening illness or injury or permanent impairment to a body structure or a body function.
3. Led to fetal distress, fetal death or a congenital anomaly or birth defect

11.2.4 Serious Adverse Device Effect

Per ISO14155:2011 3.36, a Serious Adverse Device Effect (SADE) is an adverse device effect that has resulted in any of the consequences characteristic of a SAE.

Examples of SADE for the TIGER Study include vessel dissections or perforations caused by the Tigertriever Revascularization Device.

